# PROTOCOL AMENDMENT SUMMARY

### PROTOCOL SYNOPSIS

Name of Sponsor: Aldeyra Therapeutics, Inc.

Protocol Number: ADX-629-CC-001

## Title of the Trial:

A Randomized, Double-Blind, Placebo-Controlled, Two-Period Crossover, Phase 2 Clinical Trial to Evaluate the Safety, Tolerability, and Efficacy of ADX-629 Administered Orally to Subjects with Chronic Cough

Short Title: ADX-629 versus placebo in chronic cough

**Investigational Product:** ADX-629

**Phase of Development: 2** 

# **Participating Countries and Number of Sites:**

Approximately 10 sites in the United States of America (USA)

## **Trial Objectives:**

Primary Objective:

• To evaluate the safety and tolerability of ADX-629 300 mg, administered orally twice daily (BID) for 2 weeks in adult subjects with refractory or unexplained chronic cough

### Secondary Objectives:

- To evaluate the efficacy of ADX-629 300 mg administered orally BID for 2 weeks, in adult subjects with refractory or unexplained chronic cough
- To investigate the effect of ADX-629 300 mg administered orally BID for 2 weeks on the cough-related quality of life of adult subjects with refractory or unexplained chronic cough

## **Trial Design:**

ADX-629-CC-001 is a Phase 2, multicenter, randomized, double-blind, placebo-controlled, two-period crossover trial to evaluate the safety, tolerability, and efficacy of ADX-629 300 mg administered orally BID for 14 days to approximately 50 adult subjects with refractory or unexplained chronic cough.

Subjects will be screened over a period of up to 3 weeks. Eligible subjects will be randomized to one of two treatment sequences. Subjects in one sequence will receive ADX-629 in Treatment Period 1 and matching placebo in Treatment Period 2, while subjects in the other sequence will receive the matching placebo in Treatment Period 1 and ADX-629 in Treatment Period 2. Within each treatment period, subjects will receive their allocated treatment for 2 weeks. Each subject will have a washout period of 14 days  $\pm 2$  days between the two trial periods and will undergo an end-of-trial visit approximately 14 days after the

CONFIDENTIAL Page 5 of 68

last dose of trial treatment. Subjects will be required to attend visits for screening and at the start and end of each treatment period. Each visit will require the subject to attend the clinic, or be visited by research staff, on consecutive days. At screening, on Day 0, and Day 13 of each treatment period, the subject will be fitted with a cough recorder to collect cough count data over a period of 24 hours. On the consecutive day, the cough recorder will be removed once the 24-hour recording has been completed. The trial will include five cough recorder sessions in total.

The trial duration for each subject will be approximately 11 weeks as follows: up to 3 weeks for screening, 2 weeks for each treatment period, 14 days  $\pm 2$  days washout between treatment periods, and an end-of-trial visit approximately 14 days after the last dose of trial treatment.

# **Number of Subjects:**

Approximately 50 subjects are planned for enrollment.

## **Subject Population:**

Inclusion Criteria:

Subjects who fulfill all of the following criteria (as applicable) are eligible for enrollment in the trial:

- 1. Male or female adults ( $\geq 18$  to  $\leq 80$  years of age at screening).
- 2. Written informed consent must be provided before any protocol-specific screening procedures are performed.
- 3. History of refractory or unexplained chronic cough for >1 year prior to screening that is unresponsive to at least 8 weeks of targeted treatment for identified underlying triggers including reflux disease, asthma, and post-nasal drip; or for which no objective evidence of an underlying trigger can be determined after investigation.
- 4.
- 6. Chest radiograph or computed tomography (CT) scan performed within 5 years before screening and after the onset of chronic cough that does not demonstrate any abnormality considered to be significantly contributing the chronic cough, in the opinion of the Investigator
- 7. Females of childbearing potential (i.e., ovulating, pre-menopausal, and not surgically sterile) who:
  - a. have a negative serum pregnancy test at screening,
  - b. are not breastfeeding or lactating, and
  - c. agree to use a highly effective method of acceptable contraceptive for the trial duration and at least 30 days after the last dose in the trial.

CONFIDENTIAL Page 6 of 68

- 8. Females of non-childbearing potential must be either surgically sterile (i.e., hysterectomy, bilateral tubal ligation, salpingectomy, or bilateral oophorectomy at least 26 weeks prior to screening) or post-menopausal, defined as spontaneous amenorrhea for at least 1 year, with follicle-stimulating hormone (FSH) blood levels of equal or greater than 40 mIU/mL at the Screening Visit.
- 9. Males who are surgically sterile, or:
  - a. males with female partners of childbearing potential who agree to use a highly effective method of acceptable contraceptive for at least 30 days after the last dose in the trial, and
  - b. agree to abstain from sperm donation through 30 days after administration of the last dose of the trial treatment.

#### Exclusion Criteria:

Subjects who fulfill any of the following criteria are not eligible for enrollment in the trial:

1. Current smoker (e.g., cigarettes, e-cigarettes, nicotine patches) including cannabis products; or previous smoker having given up smoking ≤12 months before screening or has a history of smoking >20 pack-years or the equivalent nicotine strength at any time or has positive cotinine test results at screening.

- 3. Active upper respiratory tract infection or recent significant change in pulmonary status that, in the opinion of the Investigator, could affect the conduct or outcome of the trial and that is documented by a physician within 4 weeks before the first dose of trial treatment.
- 4. Uncontrolled hypertension with systolic blood pressure ≥160 mmHg or diastolic blood pressure ≥90 mmHg at screening.
- 5. Prolonged QT interval corrected for heart rate using Fridericia's formula (QTcF) >440 ms or shortened QTcF <340 ms at screening, or history of significant tachycardia, bradycardia, acute or chronic cardiovascular disease or any clinically significant abnormalities in rhythm, conduction, or morphology of the resting electrocardiogram (ECG).

CONFIDENTIAL Page 7 of 68

- 6. Elevated alanine aminotransferase (ALT), aspartate aminotransferase (AST), or bilirubin levels >2.0 × upper normal limits.
- 7. History or presence of gastrointestinal, hepatic disease, or any other condition known to interfere with absorption, distribution, metabolism, or excretion of drugs.
- 8. Acute or chronic renal disease or medical history of renal disease with estimated glomerular filtration rate (eGFR) ≤30 mL/min/1.73 m² calculated by Chronic Kidney Disease Epidemiology (CKD-EPI) equation or spot urine protein to creatinine ratio (sUPCR) >2000 mg/g (226 mg/mmol, as an estimate of approximate proteinuria >2 g/day) at screening.
- 9. History of any malignancy within 5 years of screening except for basal cell or squamous cell in situ skin carcinomas or carcinoma in situ of the cervix that has been treated with no evidence of recurrence.
- 10. Taking disallowed concomitant medications (strong CYP1A2, CYP2B6, and CYP3A4 inhibitors) during the trial period.
- 11. History of severe hypersensitivity or ongoing clinically significant hypersensitivity to ADX-629.
- 12. User of recreational or illicit drugs or history of drug or alcohol abuse within the last 6 months, or a positive urine drug test or alcohol breath test at screening.
- 13. Positive serology test for Hepatitis B virus (HBV), Hepatitis C virus (HCV), or human immunodeficiency virus (HIV-1 and HIV-2) at screening.
- 14. Positive screening test for, or current infection with severe acute respiratory syndrome coronavirus 2 (SARS-CoV-2), or documented history of prior infection in the past 3 months prior to screening.
- 15. Current or recent participation in another interventional trial within 90 days prior to screening.
- 16. Any clinically significant abnormalities or findings from examination, tests, or medical history that may compromise subject safety. Potential issues of concern should be raised with the Medical Monitor.
- 17. Any unstable or uncontrolled acute or chronic diseases/conditions that in the Investigator's opinion could affect the conduct or outcome of the trial.
- 18. Currently taking an angiotensin converting enzyme inhibitor (ACEI) or has used an ACEI within 3 months of screening.

CONFIDENTIAL Page 8 of 68

## **Investigational Product, Dose, and Mode of Administration:**

The investigational product is ADX-629 300 mg tablets. Subjects will take 300 mg (one tablet) BID for 14 days.

Subjects will be randomized to one of two treatment sequences. Subjects in one sequence will receive ADX-629 in Treatment Period 1 and matching placebo in Treatment Period 2, while subjects in the other sequence will receive the matching placebo in Treatment Period 1 and ADX-629 in Treatment Period 2. Within each treatment period, subjects will receive their allocated treatment for 2 weeks.

## Reference Product, Dose, and Mode of Administration:

Placebo tablets to match ADX-629 300 mg tablets. Subjects will take one tablet BID for 14 days.

#### **Duration of Treatment:**

The duration of intake of trial medication will be 28 days (14 days ADX-629, 14 days placebo); the trial duration for each subject, including screening, washout, and end-of-trial visit, will be approximately 11 weeks.

# **Endpoints:**

Primary Endpoints:

- Incidence and severity of treatment-emergent adverse events (TEAEs) and serious AEs (SAEs)
- Observed values and changes from baseline of:
- Laboratory safety parameters
- Vital signs
- 12-lead ECG parameters

Key Secondary Endpoint for Assessment of Efficacy:

- Change from baseline in awake cough frequency per hour after 2-week treatment
- Secondary Endpoints:
  - Change from baseline in 24-hour cough frequency per hour after 2-week treatment
  - Change from baseline in cough severity using a VAS
  - Change from baseline in Leicester Cough Questionnaire (LCQ) scores
  - Change from baseline in Cough-Specific Quality of Life Questionnaire (CQLQ) scores
  - Global rating of change scores for cough severity and frequency
  - Patient Global Impression of Change (PGIC) score
  - Clinician Global Impression of Change (CGIC) score

CONFIDENTIAL Page 9 of 68

## **Safety:**

During the trial, safety will be assessed by evaluation of the following:

- Physical examination, including review of the major body systems, height, and weight
- Vital signs including blood pressure, heart rate, respiratory rate, temperature, and oxygen saturation
- Standard 12-lead ECG
- Laboratory parameters (including hematology, serum biochemistry, urinalysis, and urine/serum pregnancy testing)
- All AEs occurring after the subject signs the informed consent form and up to the last trial visit will be recorded

## **Efficacy:**

The key secondary efficacy endpoint is change from baseline in awake cough frequency (cough count/duration of measurement [hours]). For each treatment period, baseline is the cough frequency during the recorder assessment just prior to initiation of investigational product. Though summaries will be presented for cough frequencies, due to the skewed nature of the data, a log transformation will be used prior to statistical analyses.

### **Statistical Methods:**

Allowing for a reduction in power due to subject withdrawals, approximately 50 subjects will be randomized.

The key secondary efficacy endpoint, change from baseline in awake cough frequency, will be analyzed using a mixed-effect model suitable for the crossover design. A mixed-effect model suitable for the crossover design will be used to make comparisons between the two treatment groups in the changes from baseline of the natural log data. The model will include fixed effects for treatment sequence, period, treatment, and subject nested within treatment sequence as a random effect. Period specific baselines will be included as covariates. The secondary efficacy endpoint change from baseline in 24-hour cough frequency will be analyzed using the same methods described for the key secondary efficacy endpoint.

CONFIDENTIAL Page 10 of 68

Other efficacy endpoints will be summarized and analyzed to estimate the treatment effect and corresponding 95% confidence interval using a similar model to that described for awake cough frequency. Cough frequency endpoints will be analyzed on the natural log scale.

Treatment-emergent adverse events will be summarized by treatment group and by system organ class and preferred term, in accordance with the Medical Dictionary for Regulatory Activities coding dictionary. Safety variables will be summarized descriptively by treatment.

All statistical testing will be at the 5% level of significance (2-sided) and all point estimates for the comparison between treatment groups will be accompanied by 2-sided 95% confidence intervals.

The intent-to-treat (ITT) population will be the primary analysis population for efficacy. All safety analyses will be based upon the safety set, i.e., all subjects who receive at least 1 dose of trial treatment.

Statistical methods will be detailed in the Statistical Analysis Plan, which will govern any statistical language within the protocol.

CONFIDENTIAL Page 11 of 68

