## 4.2 Endpoints

# 4.2.1 Primary Endpoints

The primary endpoints of this trial are:

- Incidence and severity of TEAEs and serious adverse events (SAEs)
- Observed values and changes from baseline of:
  - Laboratory safety parameters
  - Vital signs
  - 12-lead electrocardiogram (ECG) parameters

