#### 10.2.3 Data Summaries

All endpoints will be summarized by treatment group and visit. Baseline data will be summarized by treatment sequence and by treatment group.

Continuous data will be summarized using descriptive statistics (e.g., mean and standard deviation) and categorical data will be summarized using frequency tables (counts and percentages).

CONFIDENTIAL Page 57 of 68

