## 10.5 Analysis of Safety Data

No imputation will be used for handling missing data, with the exception of conservative approaches taken for missing AE information (e.g., intensity). Details of such conventions will be documented in the SAP.

TEAEs will be summarized by treatment group and by system organ class and preferred term, in accordance with the MedDRA coding dictionary. Safety variables will be summarized descriptively by treatment. The number of subjects reporting each AE preferred term will be tabulated for all TEAEs and separately for those considered as at least possibly related to trial treatment by the Investigator.

Changes from baseline in laboratory parameters, vital signs and ECG data will be summarized by treatment group and timepoint. Baseline will be taken as the last measurement prior to dosing within the specific trial period.

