The categorization into low-normal-high (below lower reference range/ within reference range/ above upper reference range) of each result will also be summarized for each visit, presenting the number and percentage of subjects in each category.

Pregnancy (or follicle-stimulating hormone [FSH] levels), serology, and alcohol breath test results will not be summarized but provided in data listings.

A separate listing of any abnormal laboratory measurements recorded throughout the study will be provided.

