#### 15.5 Electrocardiogram

Standard 12-lead ECGs will be performed at Screening, Day 1 and Day 14 of each treatment period, and End of Trial.

The following parameters will be collected:

- RR interval (sec)
- PR interval (msec)
- QRS (msec)
- QT (msec)
- QTcF (msec)

Descriptive statistics at baseline and at each post-baseline time point and changes from baseline will be summarized for each ECG parameter by treatment group. Baseline is defined as the pre-dose value on the first day of administration for each period.

ECG parameters will be summarized overall using descriptive statistics at study baseline and End of Trial, including change from baseline. Here, baseline is defined as the last non-missing measurement (scheduled, unscheduled, or repeat) collected before the first administration of study treatment in the study.

Overall interpretation results for ECGs will be summarized using shift tables (normal, abnormal not clinically significant [NCS], and abnormal clinically significant [CS]) comparing baseline to follow-up by treatment group. The percentages for the shift table will be calculated relative to the number of subjects that have both a baseline and follow-up assessment available at each visit.

ECG data will be listed for all subjects in the Safety population.

[figure not shown]

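### The laboratory low/normal/high table gives counts per visit, with no stated treatment split and no cross-tabulation against period baseline, so it generally cannot show how many subjects became abnormal on each treatment

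*Protocol*

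**What the plan says.** Protocol 4.2.1 lists "Laboratory safety parameters" among the primary endpoints, as observed values and changes from baseline. The protocol sets the layout of safety summaries in three places:

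- Synopsis, Statistical Methods: "Safety variables will be summarized descriptively by treatment".
- Section 10.2.3: "All endpoints will be summarized by treatment group and visit".
- Section 10.5: "Changes from baseline in laboratory parameters, vital signs and ECG data will be summarized by treatment group and timepoint".

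SAP 15.2 follows this for the descriptive statistics at period baseline and Day 14, for changes from period baseline, and for categorical urinalysis, all by treatment group. For the low/normal/high classification against the reference range it says only that the categorization "of each result will also be summarized for each visit, presenting the number and percentage of subjects in each category". That sentence mentions neither treatment group nor baseline category. Abnormal values are also to be listed. SAP 15.2.1 adds Day 14 LDL-C categories by treatment group.

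For ECG interpretation, SAP 15.5 plans a shift table "comparing baseline to follow-up by treatment group", with percentages taken over subjects who have both assessments.

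**The concern.** A table of laboratory categories in a safety trial should answer one question: how many subjects moved out of range while on ADX-629, and how many while on placebo? The table as described counts everyone who is out of range at a visit, including those who were out of range before dosing.

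Such subjects can be enrolled. Exclusion criterion 6 removes subjects only when ALT, AST or bilirubin exceeds 2.0 times the upper limit, so by itself it admits values between 1 and 2 times that limit.

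The adverse event tables will not reliably fill the gap. Protocol 8.3.1.2 records a laboratory abnormality as an adverse event only when it is medically relevant: with symptoms, needing treatment, leading to discontinuation, or meeting a seriousness criterion. A silent move from normal to high may therefore appear only in a listing. ECG, which has the same primary-endpoint status, gets a baseline-to-follow-up shift table; in the readable text, laboratory results do not.

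**Working it through.** The plan gives no figure to reproduce. The check asks what per-visit counts can reveal if they are already split by treatment, which is the reading most favourable to the plan.

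**Setup.** For one parameter and one treatment, take n subjects with both a period-baseline and a Day 14 value. Let b0 be the number abnormal at period baseline, b1 the number abnormal at Day 14, and x the number who are normal at baseline and abnormal at Day 14. A per-visit table reports b0 and b1. The safety question is about x.

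**Bounds.**
- The subjects abnormal at both times number b1 − x. This must lie between 0 and b0, so x is at least b1 − b0 and at most b1.
- The newly abnormal come from those normal at baseline, so x is at most n − b0.
- Together: max(0, b1 − b0) ≤ x ≤ min(b1, n − b0).

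**Inputs.** n = 50 is the planned enrolment (Protocol 6.2), taking every subject to have both values on the treatment. The documents give no abnormal counts, so b0 and b1 are assumptions chosen to show the range.

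| Abnormal at period baseline (b0) | Abnormal at Day 14 (b1) | Lower bound | Upper bound | Newly abnormal (x) |
|---|---|---|---|---|
| 10 | 10 | max(0, 0) = 0 | min(10, 40) = 10 | 0 to 10 |
| 5 | 8 | max(0, 3) = 3 | min(8, 45) = 8 | 3 to 8 |
| 2 | 6 | max(0, 4) = 4 | min(6, 48) = 6 | 4 to 6 |
| 0 | 6 | max(0, 6) = 6 | min(6, 50) = 6 | exactly 6 |

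**Reading.** In these examples the count is fixed only in the row where nobody is abnormal at baseline. In the first row, both treatments could show 10 of 50 before and 10 of 50 after, while one produced 10 new abnormalities (10/50 = 20%) and the other none. Day 1 of each period is a scheduled laboratory visit, so the baseline distribution would appear in the table, but only as a margin. The transitions are not recoverable from two margins.

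**Treatment split.** Set beside the protocol rules quoted above, the SAP sentence is silent. Three features of the SAP leave the layout open:
- The scheduled laboratory visits include Screening and End of Trial, which belong to no treatment column; SAP 15.2 summarises End of Trial overall.
- SAP 9 carries two sets of visit labels, one of them for by-treatment summaries, and 15.2 does not say which applies to this table.
- The table shells in Appendix D are marked as not applicable.

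**The case against.** A reader might infer that the table is meant to pool the treatments, because Visits 5 and 9 each contain one sequence on ADX-629 and the other on placebo. The documents do not support that. The SAP sentence names a time axis and says nothing about columns. The protocol rules call for a treatment split, and although the SAP governs statistical language, SAP 16 declares no change to the protocol's analyses. Where the SAP drops the split for safety data, as at End of Trial, it says so. What stands is that the split is not stated, not that it was abandoned.

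A reader might also infer that no other output shows individual laboratory shifts. That is too strong:
- SAP 8 summarises continuous variables with minimum and maximum, and SAP 15.2 applies descriptive statistics to change from period baseline by treatment, so the extreme change for each parameter appears under its treatment.
- LDL-C has its own Day 14 categories by treatment.
- Abnormal values are listed, by default sorted by sequence or treatment and by subject, so transitions could be assembled by hand.
- Medically relevant abnormalities reach the adverse event tables.

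This cover is partial. A minimum or maximum shows one extreme, not how many subjects crossed a limit. The LDL-C table has no baseline category. A listing is not a count.

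Finally, the protocol promises no laboratory shift table, and the Appendix C index is not shown, so one may be listed there. Both points are fair. They make this an improvement to the methods text rather than a breach of the protocol.

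**Conclusion.** The point holds in limited form. As described in SAP 15.2, the low/normal/high table gives per-visit margins, and these generally cannot show how many subjects became abnormal on ADX-629 compared with placebo. This remains true after the treatment split is supplied from the protocol. In the assumed example of 10 of 50 abnormal at both times, the number newly abnormal is known only to lie between 0 and 10. The logic of the bounds needs no assumption about the drug; the width of the range depends on how many subjects are abnormal at period baseline and vanishes when none are.

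The missing treatment split is an omission of wording to be clarified, not evidence of pooling. Other planned outputs give partial cover, and the conclusion is confined to the readable text. This is a cheap improvement to the summary of a primary safety endpoint. It does not threaten the validity of the trial.

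**What to change.** In SAP 15.2:

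1. State that the low/normal/high summary is presented by treatment group at the treatment-period visits. Screening and End of Trial, which have no treatment column, can stay overall.
2. Add a shift table from period-baseline category to Day 14 category (low, normal, high), by treatment group, with percentages over subjects who have both values in that period. This is the denominator rule that SAP 15.5 already uses for ECG.

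If the Appendix C index already lists such a table, a sentence in 15.2 pointing to it is enough.

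The laboratory data are already collected at Visits 3, 5, 7 and 9, so nothing new is needed from sites or subjects. The cost is a short addition to the SAP text and one extra table.
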